OCT: optical coherence tomography

PCI: percutaneous coronary intervention

SAE: serious adverse event

SAQ: Seattle angina questionnaire

TCFA: thin cap fibroatheroma

TVR: target vessel revascularization

VOCE: vessel-oriented cardiac adverse events

1. SYNOPSIS

Study title	Verona coronary physiology interventional registry (VR-CP)
Protocol version	V1
Date	March, 1 st 2025
Study sponsor	Azienda Ospedaliera Universitaria Integrata di Verona
Study principal investigator	[name] MD PhD
Patient population	The observational Verona Coronary Physiology Interventional Registry (VR-CP) study enrolls patients with suspected coronary artery disease who underwent coronary angiography with functional assessment (coronary physiology).
Primary objective	The primary objective is to assess the functional characteristics of coronary lesions documented during coronary angiography and correlate them with the risk of cardiovascular events during follow-up.
Secondary objective	
- To examine the prognostic value of physiological parameters (FFR and angiography-derived FFR).- To analyze the clinical, demographic, and angiographic characteristics of patients with coronary lesions assessed by coronary physiology parameters, in order to identify high-risk subgroups.- To correlate coronary physiology values with angina symptoms.- To compare invasive FFR with angiography-derived FFR.- To compare clinical outcomes between patients managed conservatively and those undergoing invasive interventions.
Study design	The VR-CP study is a single-center observational study enrolling consecutive patients with coronary stenoses documented during coronary angiography and functionally assessed with coronary physiology (fractional flow reserve [FFR] or angiography-derived FFR) performed for suspected ischemic heart disease. Follow-up is conducted, after obtaining informed consent, through telephone contact and/or outpatient visits. Adverse events are adjudicated by an independent clinical events committee, blinded to clinical data.
Data source	The selection of eligible patients is extracted from registries and the analysis of coronary angiographic studies performed from January 2010 to December 2024.
Sample size	Enrollment will include approximately 1,000 patients evaluated with FFR or angiography-derived FFR. This sample size will allow for subgroup analyses stratifying lesions by functional severity based on FFR values.
Inclusion criteria	
- Coronary angiography with functional assessment by FFR or angiography-derived FFR (index procedure)- Provision of written informed consent- Age \geq18 years old at the time of the index procedure

Exclusion Criteria	
- Inability to provide informed consent to participate in the study
Informed Consent	Patients identified as eligible for the protocol will be invited to provide informed consent for participation in the retrospective study through contact by telephone, e-mail, mail, or during an outpatient visit.
Study Procedures	Once eligibility for the protocol is confirmed, informed consent is requested and obtained. After enrolment, the angiographic images from the index coronary angiography are analysed by the investigators. Long-term follow-up is performed by monitoring the clinical status and recording major adverse cardiac events through review of medical records, outpatient visits, or telephone contacts.
Primary Endpoint	Composite of vessel-oriented composite endpoint (VOCE), including target vessel revascularization (TVR), target vessel-related myocardial infarction (MI), and cardiovascular death.
Secondary Endpoints	
- Individual components of the primary endpoint- Hospitalization for unstable angina- Angina status (Seattle Angina Questionnaire)- Number of prescribed antianginal medications
Study Duration	Patients are retrospectively enrolled from January 2010 to December 2024. Clinical contact (medical records, outpatient visits, telephone communication) is periodically collected recording longitudinal data at 12-month intervals.
Clinical Event Adjudication Committee	The following events are adjudicated by an independent committee blinded to clinical data: TVR, target vessel-related MI, cardiovascular death, and hospitalization for unstable angina.

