3. STUDY DESIGN

The Verona Coronary Physiology Interventional Registry (VR-CP) study is a single-center, single-arm, observational study with blinded event adjudication. VR-CP enrolls patients who underwent coronary angiography for suspected ischemic heart disease, in whom at least one coronary lesion was identified and functionally assessed by coronary physiology testing (fractional flow reserve [FFR] or angiography-derived FFR).

Eligible patients are identified through registry data and review of coronary angiographic studies performed from January 2010 to December 2024. Patients meeting inclusion criteria are invited to provide written informed consent to participate in the observational study. Recruitment may occur through telephone, mail, email, or during outpatient visits. All study data are recorded in an anonymized electronic case report form (eCRF).

The follow-up involves periodic recording of the clinical status and reporting of any adverse events through review of medical records, outpatient visits, or telephone communications, in order to ensure longitudinal data collection at 12-month intervals.

Adverse events are adjudicated by an independent Clinical Event Committee (CEC) blinded to all patient clinical data. Investigators will provide the CEC with anonymized clinical documentation relating to the reported adverse event. The CEC will adjudicate events that are part of the study's primary and secondary endpoints. Event definitions and adjudication rules are established by the

Principal Investigators and recorded in the Adjudication Committee Charter. The adjudication outcomes determined by the CEC will be used for the final statistical analysis.

CEC members will be appointed by the Principal Investigator at the time of study activation. They will be selected among experienced cardiologists with no access to the clinical documentation of enrolled patients.

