6. DESCRIPTION OF THE DISEASE IN THE STUDY

Ischemic Heart Disease and General Information on Coronary Angiography

The selection of eligible patients is based on the review of hospital registries and the analysis of coronary angiography procedures performed from January 2010 to December 2024.

Participants with suspected CAD undergo coronary angiography as part of the standard diagnostic and therapeutic pathway, in accordance with current guidelines for the management of ischemic heart disease. A patient is considered eligible if at least one mild or intermediate coronary stenosis is identified on angiographic assessment and subsequently evaluated with a coronary physiology test (fractional flow reserve [FFR] or angiography-derived FFR). These functional assessments guide the operator's decision to proceed with or defer vessel revascularization.

If a physiological evaluation of CAD is performed, the corresponding data — including FFR and/or angiography-derived FFR — are collected and recorded. The initial angiogram of all patients will be stored, anonymized, and kept locally for functional analysis (acceptable formats include CD, DVD, or digital files).

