8. PLANNED PROCEDURES AND DATA COLLECTION

The VR-CP study is a retrospective observational study enrolling consecutive patients who underwent coronary angiography for suspected ischemic heart disease and were found on angiographic examination to have coronary lesions evaluated using coronary physiology testing (FFR or angiography-derived FFR). These physiology assessments guided the decision to proceed with or defer target vessel revascularization.

Regardless of whether the lesion was treated invasively or managed conservatively, patients' clinical status and any adverse events are periodically recorded.

[figure not shown]
This retrospective follow-up is conducted through the collection of information from medical records, direct contact during outpatient visits, or via telephone communications, in order to ensure longitudinal data collection at 12-month intervals.

Fig. 1
Summary of Activities Performed

Flowchart

Fig.2 Retrospective Observational Study Design

*at the time of index procedure

DATA MANAGEMENT AND PROCEDURES TO ENSURE DATA CONFIDENTIALITY

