10. STUDY DURATION

Recruitment: Once eligibility for the protocol is confirmed, informed consent is requested and obtained, and the patient is then enrolled in the study.

Patient involvement: Enrollment includes patients undergoing coronary angiography from January 2010 to December 2024.

Follow up: Follow-up will be maintained until all patients have completed a clinical evaluation at 10 years.

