13. LIMITATIONS AND BIASES

The VR-CP retrospectively enrolls patients who underwent coronary angiography documenting at least one mild to intermediate coronary lesion assessed by coronary physiology tests (FFR or angiography-derived FFR). The retrospective enrolment may not be fully representative of the general population or could be influenced by prior clinical decisions, thus introducing selection bias. To mitigate this issue, consecutive patients are enrolled, ensuring a more representative and generalizable sample. This approach minimizes the influence of selection bias, investigator bias, and temporal bias, improving the logistical simplicity and scientific rigor of the study. Our goal is to ensure that the sample reflects the typical patient population encountered in routine clinical practice.

Another limitation is that historical data might reflect medical practices or diagnostic techniques that are no longer routinely used or have evolved over time, limiting the generalizability of the results.

An independent Clinical Event Committee (CEC) evaluates all endpoints. The CEC members and management team are fully blinded to patients' identifying information. The CEC adjudicates events based on predefined definitions. Additional measures to prevent or minimize bias include the use of objective criteria for endpoint classification. Finally, unlike prospective randomized studies, this retrospective study does not include randomization, which may lead to uneven distribution of risk factors.

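### Angiography-derived FFR computed after enrolment is read without stated masking to wire FFR, treatment or known events, which can bias its link with VOCE and inflate its agreement with wire FFR

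*Protocol*

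**What the plan says.** The Synopsis (Study Procedures) sets the order of work: eligibility, consent, then reading. "After enrolment, the angiographic images from the index coronary angiography are analysed by the investigators". Section 6 gives the purpose of the images: "The initial angiogram of all patients will be stored, anonymized, and kept locally for functional analysis". Functional lesion characteristics are the exposure of the primary objective (Section 4). Comparing invasive with angiography-derived FFR is a secondary objective.

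On timing, Section 10 states: "Enrollment includes patients undergoing coronary angiography from January 2010 to December 2024". The protocol is dated March 2025. Follow-up continues after the reading: "Follow-up will be maintained until all patients have completed a clinical evaluation at 10 years".

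On masking, Section 3 states: "Adverse events are adjudicated by an independent Clinical Event Committee (CEC) blinded to all patient clinical data". Section 13 repeats the committee's role ("An independent Clinical Event Committee (CEC) evaluates all endpoints") and adds: "The CEC members and management team are fully blinded to" information that identifies patients. That last statement concerns identity, not outcome, treatment or wire FFR. No section masks the angiogram readers to any of these three.

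On physiology obtained at the time of the procedure, Section 8 states: "These physiology assessments guided the decision to proceed with or defer target vessel revascularization".

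**The concern.** In a retrospective registry the exposure can be measured after the outcome. Here a reader at the single centre may know that a vessel was later revascularized or infarcted, how the lesion was treated, or what the pressure wire showed. A small unconscious tilt of the reading in vessels with known events would produce or strengthen an association between low angiography-derived FFR and VOCE. A reader who knows the wire value can also read toward it, which narrows the differences in the agreement comparison. This second route does not depend on how many events are known.

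Section 13 credits consecutive enrolment with reducing investigator bias. Consecutive enrolment governs who enters the registry and does nothing about how an image is read. The other safeguards listed there (event committee, predefined definitions, objective classification) all act on the endpoint.

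**Working it through.** **What is on record at the reading**

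| Item | Known when the image is read? | Basis |
|---|---|---|
| Treatment given or deferred | Yes | Decided at the index procedure (Section 8) |
| Wire FFR, where measured | Yes | Recorded at the index procedure (Sections 6 and 8) |
| TVR and MI before enrolment | Can be known | Procedures 2010–2024, protocol March 2025 |
| TVR and MI after the reading | No | Follow-up runs to 10 years (Section 10) |
| The patient's own cardiovascular death | Normally no | Consent precedes enrolment and reading |

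**Which values can be affected**

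Wire FFR, and any angiography-derived FFR computed at the index procedure, were fixed before follow-up began. Only values computed or recomputed after enrolment are exposed. The protocol does not give their share.

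**Size, as an illustration**

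The protocol has no figure of its own to reproduce on this point. The following inputs are assumptions: FFR SD 0.10; 150 or 250 events among 1,000 patients over the whole follow-up; no true association; a downward reading shift of 0.01 or 0.02 in vessels with a known event. For scale, Section 2 cites an SD of 0.068 for the difference between the two FFR methods.

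- Average shift in event patients: d = shift × share read retrospectively × share of events known
- Standard error: SE = 0.10 × √(1/e + 1/(1000 − e))
- Rejection probability of a two-sided 5% test: P(Z > 1.96 − d/SE) + P(Z < −1.96 − d/SE)

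For e = 150, SE = 0.10 × √(1/150 + 1/850) = 0.00886. For e = 250, SE = 0.10 × √(1/250 + 1/750) = 0.00730.

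| Read retrospectively | Events known | Shift | d | d/SE (150; 250 events) | False-positive rate |
|---|---|---|---|---|---|
| half | half | 0.01 | 0.0025 | 0.28; 0.34 | 5.9%; 6.4% |
| half | half | 0.02 | 0.005 | 0.56; 0.68 | 8.7%; 10.5% |
| all | half | 0.01 | 0.005 | 0.56; 0.68 | 8.7%; 10.5% |
| all | half | 0.02 | 0.01 | 1.13; 1.37 | 20%; 28% |
| all | all | 0.01 | 0.01 | 1.13; 1.37 | 20%; 28% |
| all | all | 0.02 | 0.02 | 2.26; 2.74 | 62%; 78% |

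The spurious hazard ratio per 0.10 lower FFR is approximately exp(0.10 × d / 0.10²). That is exp(0.2) = 1.22 in the last row and exp(0.05) = 1.05 at d = 0.005.

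**Cross-check with the protocol's own 12-month rates**

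Section 11 gives 6.1% to 6.7% and 1,000 to 1,200 patients, that is 1,000 × 0.061 = 61 to 1,200 × 0.067 = 80 events. With all exposures read retrospectively and an assumed SD of 0.08 to 0.10:

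- all events known: 12–19% at a shift of 0.01 and 33–58% at 0.02;
- half the events known: 7–8% and 12–19%.

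The whole-follow-up analysis in Section 12 will include more events than the 12-month count, so the main table uses higher counts.

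**The case against.** The strongest reply is that the primary exposure is largely out of reach of this bias. Eligibility already requires FFR or angiography-derived FFR, and those assessments guided treatment on the day. A reader might infer from the Synopsis sentence that outcome knowledge could create the FFR–VOCE association as a whole. The documents do not support that, because a later reading cannot change a value recorded at the index procedure. This part of the objection stands, and it limits the point to retrospective readings. Section 6 indicates that such readings are intended, for all patients' initial angiograms, but does not say whether they replace index values.

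A reader might also infer that outcomes are fully known at reading. They are not: consenting patients are alive, recent patients have short histories, and follow-up runs to 10 years. The all-events-known rows are therefore an upper bound.

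Anonymized images lower the risk, and that stands too. It does not amount to masking, because investigators at the same centre handle recruitment and supply event documents to the committee (Section 3), and no section separates those tasks from reading. Equally, the protocol does not say that the same individual does both; overlap is possible, not stated.

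Two further mechanisms might be assumed: that operator choices of frame and contour move the result, and that stents visible in the run reveal treatment. The protocol describes neither, and Section 6 refers to the initial angiogram. The point does not rest on them.

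Finally, the protocol is silent rather than explicit about unmasked reading, and a manual not shown may cover it. But the protocol does fix who reads and when, and it sets out masking for others, so readers' access to data belongs there as well.

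**Conclusion.** The concern holds in limited form. As written, the protocol allows investigators to compute angiography-derived FFR with access to wire FFR, treatment and earlier TVR or MI. This can bias the association of those retrospective values with VOCE and can inflate their agreement with wire FFR. Index-procedure values are untouched.

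The size cannot be fixed from the documents. Under the stated assumptions the false-positive rate runs from about 6% to 10.5% (half of exposures retrospective, half of events known) up to 20–28% or 62–78% (everything retrospective, everything known, shift 0.01 or 0.02). The upper figures should not be quoted without those conditions. The calculation also assumes that the share read retrospectively is the same in patients with and without events. The inflation of agreement was not quantified.

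This is a worthwhile, inexpensive improvement, best made before reading starts: values read unmasked can be repaired only by re-reading.

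**What to change.** In Sections 6 and 8, state that:

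1. retrospective angiography-derived FFR is computed on coded index images by an existing investigator who has no access to that patient's wire FFR, treatment or events;
2. the values are locked before they are linked to event data;
3. each value is flagged as obtained at the index procedure or retrospectively, and a sensitivity analysis of the association with VOCE is limited to index-procedure values.

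Section 13 should then list exposure reading among the sources of bias and refer to these steps.

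The cost is a changed order of work and data access within the existing team, and a short delay before linkage. No extra patients or readers are needed.

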2. INTRODUCTION

Integrated assessment of lesion hemodynamic impact and high-risk plaque features: an unmet clinical need.

Coronary artery disease (CAD) is one of the leading causes of morbidity and mortality in developed countries [1]. Coronary angiography remains the gold standard for diagnosing CAD, however, its ability to differentiate ischemic from non-ischemic lesions is limited [2]. Relying solely on the anatomical evaluation through coronary angiography fails to reveal the hemodynamic significance of epicardial CAD [3]. The 2-dimensional representation of the arterial lesion provided by angiography is limited in distinguishing intermediate lesions that require stenting from those that simply need appropriate medical therapy [4]. In the current era of drug-eluting stents (DES), when percutaneous coronary revascularization is achieved with high success rates, low complication rates, and excellent long-term patency, it might be tempting to treat all suspect lesions with DES implantation [4]. However, procedural complications associated with percutaneous coronary intervention (PCI), the inherent risk of restenosis, and late stent thrombosis still exist.

Histopathological studies have demonstrated that angiographic evidence of stenosis is usually not detected until the plaque's cross-sectional area approaches 40% to 50% of the vessel's total cross-sectional area. The outer wall of the artery, encompassed by the external elastic membrane, enlarges to accommodate the growing plaque. This process of compensatory dilatation seems to be limited. When the plaque area exceeds 40% to 50% of the external elastic membrane area, the plaque begins to encroach upon the lumen. Only at this point the angiogram might reveal minimal luminal narrowing [4–7].

In this respect, coronary physiology, which consider the functional severity of coronary stenosis, outperforms the traditional diagnostic approach based solely on morphometric assessment.

Consequently, invasive wire-based solutions for physiological assessment were developed to identify ischemia-producing epicardial coronary stenoses [3, 8]. Current European guidelines emphasize the importance of performing physiological assessment for all intermediate coronary artery stenoses, including left main stenosis, side branch stenosis and serial stenoses, when functional information from non-invasive tests is lacking [9]. Moreover, in patients with multivessel CAD, PCI guided by fractional flow reserve (FFR) results in an improved outcome irrespective of available non-invasive functional test results [9]. The development of FFR and its use in guiding percutaneous intervention, has led to improved patient outcomes compared with angiography guidance alone [10]. New developments in wire-free functional coronary assessment derived from the angiogram, globally termed as functional coronary angiography (FCA), may contribute to a more widespread use of physiology to diagnose the cause of ischemia and to plan and guide coronary revascularization [11–16]. These systems are based on vessel lumen reconstructions from coronary angiography, with the aim of providing FFR-like estimates of stenosis severity, whilst not requiring pharmacological agents or intracoronary instrumentation. Different software approaches to FFR estimation derived from coronary angiography have been developed. Several studies demonstrated the good correlation between wire-based and Angiography-derived FFR with a cut-off of 0.80. In a recent meta-analysis of 16 studies, 819 patients and 969 vessels with paired FFR and Angiography-derived FFR were included. Authors found an overall satisfactory agreement (mean difference 0.009 ± 0.068 , $I^2 = 39.6$) of angiography- and wire- derived FFR. The diagnostic performance was sensitivity 84% (95%CI: 77-90, $I^2 = 70.1$), specificity 88% (95%CI: 84-91, $I^2 = 60.1$); positive predictive value 80% (95%CI: 76-85, $I^2 = 33.4$), and negative predictive value 95% (95%CI: 93-96, $I^2 = 75.9$) [15]. Several non-inferiority trials are ongoing to provide the data answer regarding Angiography-derived FFR clinical equivalence in comparison with wire-based FFR

(Tab.I). Angiography-derived FFR analyzability depends on quality of angiography, and it is feasible in around 80% of the cases.

The Vulnerable Plaque: Pathophysiology of Coronary Artery Disease Progression

Acute coronary syndromes (ACS) primarily result from the rupture or erosion of a vulnerable plaque [17]. After the first acute event, a residual risk of recurrent coronary events persists despite optimal medical therapy. Target lesion-related events mainly drive this risk during the first year. Thereafter, the risk stems from other lesions, which in most cases were only angiographically mild during the index procedure and were not considered at risk of rupture on initial coronary angiography, as demonstrated in several retrospective studies [17, 18].

Indeed, even when non-obstructive and non-flow limiting on angiographic and/or functional assessment, a coronary lesion may harbor vulnerable features not detectable by angiography that increase the risk of rupture [19].

The concept of “vulnerable plaque” was first introduced in 1989 by Muller et al., referring to plaques associated with an increased risk of destabilization, rupture, and subsequent vessel occlusion. They observed that, in most cases, the culprit vessel displayed only mild stenosis, not angiographically critical, and that thrombosis was the main mechanism of vessel occlusion. Since then, several studies have focused on defining, detecting, and analyzing plaque vulnerability[20]

In 2003, Naghavi et al. published the first consensus document to standardize definitions of vulnerable plaques, described as “all plaques prone to thrombosis and with a high likelihood of rapid progression, thereby becoming culprit plaques”. Five major vulnerability criteria were identified: 1) a thin fibrous cap with a large lipid core; 2) active inflammation within the plaque

(e.g., macrophage infiltration); 3) endothelial denudation leading to superficial platelet aggregation (e.g., plaque erosion); 4) a fissured plaque (mainly indicating recent rupture); 5) diameter stenosis >90%. Minor criteria included the presence of superficial calcific nodules, shiny yellow plaque on angioscopy, intraplaque hemorrhage, endothelial dysfunction, or outward remodeling. Multiple mechanisms contribute to plaque development and destabilization. Accumulation of low- and very-low-density lipoproteins (LDL and VLDL), lipoprotein(a)-mediated inflammation, increased expression of adhesion molecules on endothelial cells, and active inflammation are key drivers of this process. Persistent elevation of circulating lipid levels promotes the formation of vulnerable plaques with a large necrotic core and a thin fibrous cap [20–22].

If the thin fibrous cap ruptures, the lipid-rich plaque releases its thrombogenic content into the bloodstream, leading to the formation of an occlusive (or sub-occlusive) intraluminal thrombus responsible for ACS. Thus, the thickness and quality of the fibrous cap influence the risk of rupture, although the triggering factors remain incompletely understood. Proposed triggers include changes in atherosclerotic plaque components, blood influx through the vasa vasorum, and the functional integrity of the arterial intima. Degradation of the extracellular matrix in the arterial wall by matrix-degrading enzymes (e.g., matrix metalloproteinases) may further contribute. Perivascular adipose tissue (PVAT) may also be involved. Production of reactive oxygen species (ROS) and expression of intercellular and vascular adhesion molecules by endothelial cells promote active inflammation, activation of vascular smooth muscle cells, and increased release of proinflammatory cytokines and ROS. These factors activate PVAT, which responds by releasing proinflammatory adipocytokines, lipid mediators, and ROS, thus perpetuating a vicious cycle of active inflammation and atherosclerosis progression [19, 23].

The PROSPECT study, the first prospective natural-history investigation correlating plaque features with subsequent cardiovascular events, included nearly 700 patients undergoing percutaneous

coronary intervention for ACS who also underwent intravascular ultrasound (IVUS). The aim was to assess the incidence of major adverse cardiovascular events related to both the culprit lesion and an additional non-culprit lesion. It was observed that 20.4% of patients experienced an event at 3-year follow-up, equally attributable to culprit and non-culprit lesions, with most non-culprit event-related lesions being angiographically mild at baseline (mean diameter stenosis $32.3 \pm 20.6\%$). Gray-scale and radiofrequency IVUS analysis showed that the presence of a thin-cap fibroatheroma (TCFA), together with a plaque burden $>70\%$ and a minimal luminal area (MLA) $<4.0 \text{ mm}^2$, was a strong independent predictor for non-culprit lesions. Vulnerable non-culprit plaques are common in patients with multivessel disease. A secondary analysis of the COMPLETE trial showed that nearly 50% of patients with ST-segment elevation myocardial infarction (STEMI) had at least one non-culprit obstructive TCFA. Moreover, obstructive lesions ($>70\%$ diameter stenosis on visual assessment) more often contained vulnerability features than non-obstructive lesions. Another interesting study by Zhao et al. showed that, among STEMI patients who underwent optimal optical coherence tomography (OCT) imaging of all three coronary arteries, those with plaque progression at 12 months (defined as a $\geq 0.4 \text{ mm}$ reduction in minimal luminal diameter) had more high-risk plaque features (47.4% vs. 33.3%; $p = 0.036$) and more non-culprit plaque ruptures (25.6% vs. 4.5%, $p = 0.036$). [18]

The Vulnerable Plaque and the Vulnerable Patient: A Targeted Therapeutic Approach

Atherosclerosis progresses through repeated cycles of plaque rupture and healing, driven by persistent active inflammation, ultimately leading to progressive luminal narrowing. This

phenomenon is particularly pronounced in vulnerable plaques compared to stable lesions. Since inflammation promotes atherosclerosis progression, plaque destabilization, and a prothrombotic state, targeted therapeutic strategies aimed at reducing both local and systemic inflammation have been proposed and tested to improve cardiovascular outcomes.[22]

Ongoing studies are evaluating preventive strategies based on intensification of pharmacologic therapy in patients at high risk of cardiovascular events, or a combination of medical therapy with prophylactic revascularization of vulnerable plaques.[22]

With regard to medical therapy, randomized clinical trials have demonstrated that intensive lipid-lowering therapy stabilizes vulnerable plaques, either with high-dose statin therapy alone or in combination with a proprotein convertase subtilisin/kexin type 9 (PCSK9) inhibitor [19]

As for prophylactic revascularization of vulnerable lesions, robust evidence indicates that in chronic coronary syndromes (CCS), this strategy has not significantly improved long-term outcomes.

Conversely, in patients with STEMI and multivessel disease—who exhibit a higher prevalence of vulnerable plaques than those with CCS—elective treatment of non-culprit obstructive lesions has been shown to reduce the 5-year incidence of myocardial infarction and future acute coronary syndromes in the COMPLETE trial [19, 24]. Following stenting, neointimal hyperplasia generates a new fibrous cap, thickening the pre-existing one. Moreover, the use of everolimus-eluting stents has been shown in animal models to reduce plaque macrophage content. Large-scale randomized clinical trials are underway to determine whether focal therapy of imaging-identified vulnerable plaques can improve overall patient outcomes. Recently published results from the PREVENT trial—randomizing more than 1,500 patients with CCS or ACS in a 1:1 ratio to medical therapy alone or medical therapy plus revascularization (using bioresorbable vascular scaffolds or second-generation everolimus-eluting stents) of non-flow-limiting, non-culprit vulnerable plaques identified by IVUS, radiofrequency IVUS, or OCT—appear to support the interventional strategy.

At two years, the composite endpoint of cardiac death, target vessel myocardial infarction, ischemia-driven target vessel revascularization, or hospitalization for unstable or progressive angina was significantly lower in the PCI group (absolute difference -3.0%, 95% CI -4.4 to -1.8, p=0.0003) [25].

